6.3 Discontinuations

6.3.1 Discontinuations of Patients

The criteria for enrollment must be followed explicitly. If a patient who does not meet enrollment criteria is inadvertently enrolled, that patient should be immediately discontinued from the study drug unless specific approval is obtained from the IRB.

In addition, patients will be discontinued from the study drug but continued to be followed for survival data in the following circumstances:

- The patient experiences unacceptable toxicity as defined in Section 8.7 The patient is non-compliant (see Section 8.10).
- The investigator decides that the patient should be withdrawn, for example due to intercurrent illness that would, in the judgment of the investigator, affect assessments of clinical status to a significant degree. If this decision is made because of a serious adverse event or a clinically significant laboratory value, the study drug is to be discontinued and appropriate measures are to be taken. AROG or its designee is to be alerted immediately (see Section 11.1).
- The patient or attending physician requests that the patient be withdrawn from the study.
- Enrollment in any other clinical trial involving an off-label use of an investigational drug or device or enrollment in any other type of medical research judged not to be scientifically or medically compatible with this study.
- The patient, for any reason, requires treatment with another therapeutic agent that has been demonstrated to be effective for treatment of the study indication. In this case, discontinuation from the study occurs prior to introduction of the new agent.
- The investigator or AROG stops the study or stops the patient's participation in the study for medical, safety, regulatory, or other reasons consistent with applicable laws, regulations, and good clinical practice.

Patients in these circumstances will be followed as per the Study Schedule (appendix IV) and section 11.1.7.

For patients lost to follow-up or undergoing initiation of another drug therapy including allogeneic HSCT, the study schedule will be stopped but patients should be followed for survival data if at all possible.

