1.1 Primary Objectives

- Overall response rate defined as Complete remission (CR) including incomplete blood count recovery (CRi)
- Duration of response

Protocol: ARO-004

• Progression-free survival

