- 1. For patients with active relapse and given as reinduction, 200mg/m²/day divided in three doses daily (preferably every eight hours), taken orally at least 30 minutes pre or post meal. Patients will complete a daily diary to record the date, time and amount (number of tablets) of crenolanib taken and eating schedule. (Appendix III) Concurrent hydroxyurea (maximum 5g total daily dose) is permitted for the first 14 days of study therapy.
- 2. For patients continuing therapy as maintenance after allogeneic stem cell transplant (HSCT), the same dose of crenolanib most recently tolerated by the patient during induction will be restarted. Patients will complete a daily diary to record the date, time and amount (number of tablets) of crenolanib taken and eating schedule (Appendix III)

Planned Duration of Treatment:

The anticipated duration of patient involvement is a minimum of 28 days with a maximum of 365 days but assessed individually for each patient. Subjects will take crenolanib besylate daily as reinduction and may resume as maintenance after allogeneic stem cell transplant, until their disease has progressed, the patient has died, or the patient discontinues for adverse events, investigator's judgment, or other reasons.

Subjects who have discontinued will continue to be followed 30-days post last dose.

Reference Therapy, Dose and Mode of Administration:

No comparators will be used.

Criteria for Evaluation:

International Working Group for AML (Cheson, et. al., JCO, 2003)

Statistical Methods:

Protocol: ARO-004

The primary end-point is overall response rate. Descriptive statistics will be presented for all categories of each best response category. Duration of response and PFS will be listed and additionally summarized using Kaplan-Meier methodology. In addition, if at any time unacceptable toxicity is encountered in more than 33% of patients, the accrual will stop and lower doses may be investigated.

4. Abbreviations and Definitions

Adverse Event (AE)

Any untoward medical occurrence in a patient or clinical investigation subject administered a pharmaceutical product and which does not necessarily have a causal relationship with this treatment. An adverse event can therefore be any unfavorable and unintended sign (including an abnormal laboratory finding), symptom, or disease temporally associated with the use of a medicinal (investigational) product, whether or not related to the medicinal (investigational) product.

Audit

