8.12 Follow up Visits

The Study Schedule in Appendix IV lists the specific follow up visits for this study.

The Study Schedule applies to patients receiving study drug. The calendar should re-commence as start of cycle 1 when drug is resumed post allogeneic transplant. Patients who have discontinued study drug for any reason should be followed for survival.

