10.3 Statistical and Analytical Plans

The primary end-point is overall response rate. We will use tests of the binomial proportion for both response and toxicity (Section 11). Descriptive statistics will be used for progression free survival and exploratory endpoints. Duration of response and PFS will be listed and additionally summarized using Kaplan-Meier methodology.

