10.3.7 Efficacy Analysis

The primary end-point is overall response rate (detailed in section 9.1). Descriptive statistics will be presented for all categories of each best response category. Duration of response and PFS will be listed and additionally summarized using Kaplan-Meier methodology. In addition, if at any time unacceptable toxicity is encountered in more than 33% of patients the accrual will stop and lower doses may be investigated.

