- Consistency with known drug profile: Was the adverse event consistent with the previous knowledge of the suspect drug (pharmacology and toxicology) or drugs of the same pharmacological class? OR could the adverse event be anticipated from its pharmacological properties?
- De-challenge experience: Did the adverse event resolve or improve on stopping or reducing the dose of the suspect drug?

- No alternative cause: The adverse event cannot be reasonably explained by another etiology, such as the underlying disease, other drugs, other host, or environmental factors.
- Re-challenge experience: Did the adverse event reoccur if the suspected drug was reintroduced after having been stopped? Laboratory tests: Has a specific laboratory investigation confirmed the relationship?

A "reasonable possibility" could be considered to exist for an adverse event when 1 or more of these factors exist.

In contrast, there would not be a "reasonable possibility" of causality if none of the above criteria apply, or if there is evidence of exposure and a reasonable time course, but any de-challenge (if performed) is negative or ambiguous, or there is another more likely cause of the adverse event.

In difficult cases, other factors could be considered such as the following:

- Is this a recognized feature of overdose of the drug?
- Is there a known mechanism?

Protocol: ARO-004

Ambiguous cases should be considered as having a "reasonable possibility" of causal relationship, unless additional evidence becomes available to refute this.

If true progression is determined by subsequent imaging, then the date of progression returns to the earlier date with increasing mass.

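### Relapse and progression follow-up is not secured for patients who leave crenolanib without an event, so duration of response and PFS would rest on selectively observed events

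*Combined protocol and SAP*

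**What the plan says.** Section 1.1 lists "Duration of response" and "Progression-free survival" beside overall response rate as primary objectives. Section 10.3 then narrows the tested endpoint: "The primary end-point is overall response rate". For the other two, Section 10.3.7 says only: "Duration of response and PFS will be listed and additionally summarized using Kaplan-Meier methodology". No section gives a start date, event definition or censoring rule for either, and Section 9.1 does not define relapse or progression.

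Follow-up after leaving drug is described in several places:

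- **Synopsis, Planned Duration of Treatment:** "Subjects who have discontinued will continue to be followed 30-days post last dose".
- **Section 6.3.1, last paragraph,** on patients who are lost, transplanted or given other therapy: "undergoing initiation of another drug therapy including allogeneic HSCT, the study schedule will be stopped but patients should be followed for survival data". Even that is asked for only as far as feasible.
- **Section 6.3.1, after the list of discontinuation reasons:** those patients follow Appendix IV and Section 11.1.7.
- **Section 8.12:** the Study Schedule is for patients on study drug, and anyone who stops, for whatever reason, is followed for survival. It adds: "The calendar should re-commence as start of cycle 1 when drug is resumed post allogeneic transplant".

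The only written rule for dating progression is at the end of Appendix VII, on serious adverse events: "If true progression is determined by subsequent imaging, then the date of progression returns to the earlier date with increasing mass".

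**The concern.** Bridging patients to transplant is a stated secondary objective, so a successful course may well take a patient off the schedule. Stopping for toxicity, starting another therapy, going to transplant and resuming afterwards can all depend on how the disease is behaving. If relapse dates are recorded for some of these patients and not others, the Kaplan-Meier curves for two primary objectives describe a group chosen partly by outcome. Relapse dates not collected at the time may be hard to recover at analysis. With no event or censoring rule, the handling of these patients would be settled after the data are seen.

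**Working it through.** The documents state no assumption or figure for duration of response or PFS, so there is nothing to reproduce for these endpoints. Section 10.1 gives power and type I error for the response-rate test only. Those figures do not reproduce: by exact binomial, at least 2 of 14 has probability 1 − 0.85^14 − 14(0.15)(0.85^13) = 64.33% at a 15% response rate, and 1 − 0.70^14 − 14(0.30)(0.70^13) = 95.25% at 30%, against the stated 8.61% and 85.07%. That is a separate matter and does not enter this point.

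**Step 1. Follow-up by patient group**

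| Group | Governing text | Is a relapse or progression date secured? |
|---|---|---|
| Relapse seen on drug | 7.1, 8.2 | Yes. It is the reason for stopping |
| Transplant, crenolanib resumed | 8.2, 8.3, 8.7.1, 8.12 | Yes from restart: marrow at cycle 2 day 1, cycle 3 day 1, then every 3 cycles while in CR. Not scheduled during the hold around transplant |
| Transplant, not resumed | 6.3.1 last paragraph, 8.12 | No. Survival only |
| New therapy | 6.3.1 last paragraph, 8.12 | No. Survival only, although a listed reason in 6.3.1 (need for another effective agent) points to Appendix IV |
| Stopped without progression (toxicity, non-compliance, withdrawal) | 6.3.1 list against 8.12 | Conflicting |
| Withdrawn because a reduction below the lowest reinduction level would be needed | 8.7.1, referring to 8.12 | Outcomes are promised, but 8.12 names survival only |

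**Step 2. The conflict.** If the Appendix IV sentence in 6.3.1 meant the cycle-by-cycle columns, marrow would continue while CR lasts. Section 8.12 rules that out by limiting the schedule to patients on drug. If it meant only the follow-up visit, assessment ends at the 30-day evaluation (±5 days) in 11.1.7. What 11.1.7 describes after that is adverse-event follow-up. The bone marrow footnote to Appendix IV lists no off-treatment marrow.

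**Step 3. Selection among transplanted patients.** Resumption is optional. It requires CR/CRi (8.3), 30 to 90 days since transplant, and conditions on GVHD therapy and transplant toxicity (8.7.1). A patient who relapses before the restart cannot resume, so that relapse falls under survival-only follow-up. Every patient who resumes has by construction been alive and in remission at least 30 days after transplant.

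**Step 4. Direction.** If non-resuming patients are mainly early relapses and leave the risk set at transplant, early events are lost and the curve is too high. If they are mainly patients in lasting remission who do not resume for other reasons, long remissions are cut short and the curve may be too low. For PFS, a death known from survival follow-up could be counted without the progression that preceded it, dating the event late. The documents do not say which applies.

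**Step 5. Scale.** Expected responders are 14 × 0.15 = 2.1 at the null rate and 14 × 0.30 = 4.2 at the alternative (Section 10.1). One responder of 4.2 is 24% of the duration-of-response sample, and two of 2.1 is 95%. The share transplanted and the share resuming are not given.

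**The case against.** The strongest defence has four parts.

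1. **The rules partly fit together.** The 30-day line in the synopsis can be read as the adverse-event evaluation of 11.1.7, running beside survival follow-up. Stopping the calendar at transplant and restarting it on resumption is coherent. This stands, but the synopsis line does not say it is limited to adverse events, and coherence for patients who resume does not help the others.
2. **Some text provides more than survival.** Section 6.3.1 refers to Appendix IV, 8.7.1 promises outcomes, and Appendix IV appears to mark hematology at the end-of-study and follow-up visits. The Appendix IV grid is damaged in the available text, so its marrow cells for those visits cannot be read with certainty. This stands as a conflict to reconcile. It does not show that relapse dates are secured after the 30-day visit.
3. **Both endpoints are descriptive and imprecise.** With four events and exponential times, a 95% interval for the median runs from 8/17.53 = 0.46 to 8/2.18 = 3.7 times the estimate. This stands, and the decision rests on response rate. But an interval conveys sampling error, not selective observation, and Section 11.2 calls duration of response important for judging response quality.
4. **The imaging sentence is a stray line in a safety appendix.** This stands. Because 9.1 requires no extramedullary leukemia for CR, imaging is not irrelevant. Removing the sentence is an editorial matter.

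**Conclusion.** The point holds as a gap and a conflict in follow-up. For transplanted patients who do not resume crenolanib, patients starting new therapy and patients stopping without progression, relapse or progression is not clearly followed beyond the 30-day visit. Those who resume after transplant are followed but selected. Duration of response and PFS would therefore rest on selectively observed events. The expected 2.1 to 4.2 responders assume the response rates in 10.1. The size and direction of the error cannot be derived, and the response-rate test is not affected.

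A reader might infer three stronger things that the documents do not support:

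- **That relapse is not collected after transplant at all.** It is, for patients who resume, because 8.12 restarts the calendar.
- **That the plan prescribes informative censoring.** No censoring rule is written. Informative censoring is a plausible result of following the stated rules, not something the plan specifies.
- **That the bias in the median can be given as a percentage.** That needs remission times and transplant and resumption shares that the documents lack. Part of the difference between censoring at transplant and counting later events is also a choice of estimand, namely whether transplant benefit is included.

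**What to change.** - **Reconcile the synopsis, 6.3.1 and 8.12.** State that the 30-day period applies to adverse-event follow-up, and resolve the Appendix IV reference in 6.3.1 against the on-drug limit in 8.12.
- **Collect the dates.** For every patient, whatever the treatment status, record relapse or progression date and death date at survival follow-up, to the common data cut-off in 10.3.10. Take relapse dates from routine clinical care, with no added marrow. State the contact interval, since none is given now.
- **Define the endpoints in 10.3.7.** Give the start date and events for duration of response and PFS. Report each Kaplan-Meier summary twice, once counting events after transplant and once censoring at transplant, and name in advance which is primary.
- **Editorial.** Remove the imaging sentence from Appendix VII.

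The cost is amendment wording, a CRF field and some effort to obtain records from outside the study sites. Treatment and study procedures do not change.

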6.3.2 Discontinuation of Study Sites

Study site participation may be discontinued if AROG, the investigator, or the ethical review board of the study site judges it necessary for medical, safety, regulatory, or other reasons consistent with applicable laws, regulations, and good clinical practice. Sites may also be discontinued if it is unable to accrue an adequate number of patients on the trial.

6.3.3 Discontinuation of the Study

The study will be discontinued if the site IRB judges it necessary for medical, safety, regulatory, or other reasons consistent with applicable laws, regulations, and good clinical practice. The study could also be discontinued at any time at the sole discretion of the sponsor, AROG Pharmaceuticals, LLC.

7. Treatment Plan

7.1 Summary of Treatment

The study will enroll AML patients with FLT3 D835 and/or other FLT3 activating mutations. Patients in relapse will be treated with crenolanib at 200mg/m²/day divided as three times a day (preferably every eight hours) continuously until they fulfill one of the criteria for study discontinuation (see Section 6.3) or proceed to allogeneic stem cell transplant.

Patients currently enrolled at 100mg TID (protocol v3.0) can be switched to the dosing based on BSA, see table 8.4, as per investigators discretion. If patients enrolled under v3.0 are continued on their current dose without BSA based dosing, continue study procedures from the current time point as outlined under Study Schedule (Appendix IV) of this version of the protocol (v4.0)

After allogeneic HSCT, patients who received crenolanib prior to transplant may resume crenolanib as maintenance on study post-transplant, if in remission at the same dose which was tolerated at the time of study drug hold prior to HSCT.

Patients who did not receive crenolanib preHSCT will not be able to receive crenolanib as maintenance therapy under this protocol.

Patients receiving less than 28 days of study dug as induction therapy will be replaced for efficacy evaluation. All patients will be assessed for toxicity

Study drug will be stopped if patients demonstrate evidence of relapsed disease as determined by the investigator.

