Title of Study: A Phase II Study of Crenolanib Besylate in Subjects with Relapsed/Refractory Acute Myeloid Leukemia with FLT3 Activating Mutations

Number of Planned Subjects:

14 evaluable subjects

Length of Study: 3 years

Objectives:

Primary Objectives

- Overall response rate including Complete remission (CR) including incomplete blood count recovery (CRi)
- Duration of response
- Progression-free survival

Secondary Objectives:

- Safety and tolerability of crenolanib
- Pharmacokinetic analysis of crenolanib in patients with AML
- Analysis of phospho-FLT3 and other pharmacodynamic markers from serially collected circulating leukemic blasts and/or marrow blast samples
- Pharmacogenetic analyses, correlation of remission with genomic abnormalities including but not limited to mutant FLT3 allelic ratio
- Impact of crenolanib on hematological improvement, bridge to transplant, duration of leukemia control, blood and platelet transfusions, infections, days of hospitalization, performance status

Study Design:

Protocol: ARO-004

This is a Phase II open label study of crenolanib besylate. This study will enroll subjects with relapsed or refractory AML with FLT3 activating mutations. Prior treatment with other FLT3 TKIs is allowed. Subjects will take crenolanib 200mg/m²/day divided in three doses daily (preferably every eight hours), taken orally at least 30 minutes pre or post meal until disease progression, death, or the patient discontinues treatment for adverse events, investigator's judgment, or other reasons. Patients who are able to proceed to allogeneic stem cell transplant will be able to resume crenolanib therapy post-transplant in an attempt to maintain remission.

Diagnosis and Main Criteria for Inclusion and Exclusions:

Inclusion Criteria:

- Relapsed/refractory primary AML or AML secondary to antecedent hematologic disorder with an expected survival of 3 months or greater
- Patients must have tested positive for FLT3-ITD and /or other FLT3 activating mutations within < 60 days of the screening period.
- Age ≥18 years
- ECOG PS 0-2
- Adequate liver function, defined as total or direct bilirubin ≤1.5x ULN, ALT ≤3.0x ULN, AST ≤3.0x ULN. Exceptions for ALT and AST restrictions will be made in the setting of documented liver involvement with leukemia.
- Adequate renal function, defined as serum creatinine $\leq 1.5 x$ ULN
- Recovery from non-hematological toxicities of prior therapy (including HSCT) to no more than grade 1 (except alopecia)

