7.2 Study Design

Fourteen relapsed/ refractory AML patients with FLT3 activating mutations will be treated with crenolanib daily as reinduction until they meet one of the criteria for discontinuation. After HSCT, patients who received crenolanib prior to transplant and achieved response may continue on study post-transplant with maintenance crenolanib. Until they meet one of the criteria for discontinuation. Subject efficacy evaluations will be performed at scheduled time points. These include: monthly bone marrow biopsy in the first two months, and then every three months for as long as criteria for CR/CRi is maintained. At loss of CR/CRi, bone-marrow biopsy will be performed only as clinically indicated to exclude toxicity issues such as pancytopenia due to study drug versus myelosuppression from progressive AML. Subjects' best clinical response will be recorded, as well as the response at 2 months. Subjects not in CR/Cri by the end of month 2 but showing clinical benefit will be allowed to continue therapy at the discretion of the physician.

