8.2 Evaluation during Treatment and Post Allogeneic Transplant

- 1. Patient visits are weekly (± 2 days) for Cycle-1, bi-weekly (± 4 days) for Cycle-2, once every cycle (±14 days) from Cycle-3 to Cycle-6, once every two cycles (± 1 cycle) thereafter. The flexibility is applied to all instances unless specified.
- 2. Physical exam at the start of each cycle (\pm 4 days) for the first 2 cycles, then every 2 cycles and documentation of all concomitant medications.
- 3. EKG measurements to be obtained at 1 hour (± 30 mins) post first or second dose, in accordance to the visit. If new drugs with known effect on QTc are to be coadministered with crenolanib, EKGs including a baseline prior to start of the new agent and 2-3 days after starting patient on combination of drugs is recommended. Weekly EKG x3 is also recommended for follow up and as needed for assessment based on patient's clinical condition. EKG can then be resumed per study schedule.
- 4. CBC with platelet count, differential (differential may be omitted if WBC is $<0.5 \times 10^9$ /L) twice weekly (at least 24 hours apart) for the first two weeks of cycle 1, once weekly (\pm 3 days) for the second two weeks of cycle 1, bi-weekly (\pm 4 days) for the second cycle and once a month thereof from cycle 3 until cycle 12 (\pm 14 days).
- 5. Creatinine, total bilirubin, ALT, AST, twice weekly (at least 24 hours apart) for the first two weeks of cycle 1, once weekly (±3 days) for the second two weeks of cycle 1, biweekly (±4 days) for the second cycle and once a month thereof from cycle 3 until cycle 12 (± 14 days).

- 6. Bone marrow aspiration (with two additional aspirates) should be taken at these time points: cycle 2 day 1 (+4 days), then cycle 3 day 1 (+/- 4 days). Following which every 3 cycles (+/- 1 cycle) as long as criteria for CR are maintained. At loss of CR, bone-marrow biopsy would be performed only as clinically indicated to exclude toxicity issues like persistent pancytopenia due to study drug vs. from progressive AML. Aspiration sample for study purposes may also be submitted for patients not in CR if a marrow will be done for clinical purposes. Handling of bone marrow specimens is outlined in section 8.13, lab manual, and appendix XI.

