9.1 Response Criteria

Response criteria will be adapted from the International Working Group for AML.²¹ Responders are relapsed/refractory patients receiving study drug as reinduction therapy who obtain a CR, CRi, or PR, with or without cytogenetic response, hematologic improvements, and morphologic leukemia-free state. Briefly, criteria are as follows:

- 1. Complete remission (CR):
 - a. Peripheral blood counts:
 - i. No circulating blasts
 - ii. Neutrophil count $\ge 1.0 \text{ x} 10^9/\text{L}$
 - 111. Platelet count $> 100 \times 10^9 / L$
 - b. Bone marrow aspirate and biopsy:
 - i. ≤5% blasts
 - ii. No Auer rods
 - iii. No extramedullary leukemia
- 2. Complete remission with incomplete blood count recovery (CRi):
 - a. Peripheral blood counts:
 - i. No circulating blasts
 - ii. Neutrophil count $<1.0 \times 10^9/L$, or
 - iii. Platelet count <100 x10⁹/L
 - b. Bone marrow aspirate and biopsy:
 - i. < 5% blasts
 - ii. No Auer rods
 - iii. No extramedullary leukemia
- 3. Partial remission:

Protocol: ARO-004

- a. All CR criteria if abnormal before treatment except:
- b. \geq 50 % reduction in bone marrow blast but still \geq 5% or
- c. Marrow blasts <5% with persistent Auer rods
- 4. Morphologic leukemia-free state:
 - a. Bone marrow: ≤5% myeloblasts
- 5. Hematologic Improvement (HI):

Hematologic response must be described by the number of positively affected cell lines.

- a. Erythroid response (E) (pretreatment Hgb <11 g/dL)
 - i. Hgb increase by ≥1.5 g/dL
- **b.** Platelet response (P) (pretreatment platelets $<100 \text{ x} 10^9/\text{L}$)
 - i. Absolute increase of $\ge 30 \times 10^9/L$ for patients starting with $> 20 \times 10^9/L$ platelets
 - ii. Increase from $< 20 \times 10^9/L$ to $> 20 \times 10^9/L$ and by at least 100%
- c. Neutrophil response (N) (pretreatment ANC $<1.0 \times 10^9/L$)
 - i. At least 100% increase and an absolute increase $> 0.5 \times 10^9/L$

10. Statistical Considerations

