10.1 Determination of Sample Size

The FLT3-3 D835 AML activating mutations have been refractory to currently available TKIs. An upper one-sided 75% confidence bound on the fraction of such patients who might respond to no treatment or ineffective therapy is 10%.

Therefore we will treat 15% response rate as our null hypothesis and submit 14 patients to this phase II trial. If at least 2 patients respond to treatment, the null hypothesis will be rejected. If the true response rate is 30%, this design will have 85.07% power and 8.61% type I error.

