10.3.5 Treatment Compliance

Treatment compliance information will be collected through pill counts at each tumor assessment visit and also by analyzing patient diaries where patients will record their daily drug intake. The estimate of percent compliance will be given by:

The number of tablets taken will be determined by counting the number of tablets returned at each visit and subtracting that number from the number of tablets dispensed. The number of tablets expected to be taken will be determined by the assigned dose and taking into account any prescribed dose reductions and omissions.

No minimal level of compliance will be defined for patient inclusion in efficacy analyses. An exploratory analysis of compliance may be performed by regressing percent compliance on selected efficacy endpoints. If significant results are indicated, analysis may be performed to determine the level of compliance that best delineates each endpoint

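### Replacing every patient with under 28 days of induction drug, with no all-treated efficacy set, probably raises the primary response rate and leaves its denominator unclear

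*Combined protocol and SAP*

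**What the plan says.** Section 7.1 (Summary of Treatment) sets the rule: "Patients receiving less than 28 days of study dug as induction therapy will be replaced for efficacy evaluation". The next sentence keeps all patients for toxicity. No reason for stopping is named and no exception is made.

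The planned number is described in three ways. The Synopsis (section 3) plans "14 evaluable subjects" without defining evaluable. Section 7.2 says that fourteen relapsed/refractory "AML patients with FLT3 activating mutations will be treated with crenolanib daily as reinduction". Section 10.1 says: "Therefore we will treat 15% response rate as our null hypothesis and submit 14 patients to this phase II trial". The rest of section 10 names no efficacy analysis set and does not repeat the 28-day condition; only safety has an all-patient set (10.3.9).

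Section 10.3.5 adds: "No minimal level of compliance will be defined for patient inclusion in efficacy analyses". Section 8.10 discontinues a patient who takes less than 60% of the expected drug in a visit interval, and section 8.2 makes visits weekly in cycle 1.

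Section 8.2 schedules on-treatment marrows at "cycle 2 day 1 (+4 days), then cycle 3 day 1", then less often. Section 9.1 begins: "Responders are relapsed/refractory patients receiving study drug as reinduction therapy who obtain a CR, CRi, or PR". Its CR, CRi and PR criteria all use marrow findings.

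**The concern.** Whether a patient enters the efficacy denominator depends on something that happens after treatment starts and is related to outcome. Section 6.3.1 stops drug for unacceptable toxicity or need for another effective agent, section 7.1 for relapse, and section 8.9 for progression that needs other antitumor therapy. A patient who stops for one of these reasons in the first four weeks has not reached the first scheduled on-treatment marrow, so usually cannot be a documented CR, CRi or PR. Replacing such patients tends to remove failures and leave responders.

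At stake is what the primary result means. Under section 7.1 it is the response rate among patients who stayed on drug for 28 days. A reader of section 7.2 or 10.1 would take it to be the rate among patients treated. In an open-label, single-arm trial of 14, reclassifying one or two patients can change the decision. Best response, disposition and deaths are recorded, so an all-treated rate might be rebuilt afterwards, but it would not be the prespecified result.

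**Working it through.** **The plan's own figures.** Section 10.1 gives N = 14, rejection at 2 or more responders, a null of 15%, a target of 30%, type I error 8.61% and power 85.07%. The exact binomial gives P(X ≥ 2 | 14, 0.15) = 64.33% and P(X ≥ 2 | 14, 0.30) = 95.25%. Neither stated figure is reproduced. That is a separate defect; it matters here only because the written rule starts from 64.3%.

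**Inputs for the replacement effect.** p = 0.15 is the true rate among all treated, set equal to the null in 10.1. d is the share stopping before 28 days, which the documents do not give for this regimen; 10 to 40% is assumed. f is the early leavers' response rate as a fraction of p, also assumed.

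**Formula.** The rate among those retained is a = p(1 − d·f)/(1 − d). It exceeds p only when f < 1. Example: d = 0.20, f = 0 gives 0.15/0.80 = 18.75%; f = 0.5 gives 0.15 × 0.90/0.80 = 16.9%.

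| Early-stop share d | 10% | 20% | 30% | 40% |
|---|---|---|---|---|
| Reported rate, all early leavers fail (f = 0) | 16.7% | 18.8% | 21.4% | 25.0% |
| Reported rate, half the overall rate (f = 0.5) | 15.8% | 16.9% | 18.2% | 20.0% |
| Reported rate, 1.5 times the overall rate (f = 1.5) | 14.2% | 13.1% | 11.8% | 10.0% |
| Expected number treated for 14 evaluable, 14/(1 − d) | 15.6 | 17.5 | 20.0 | 23.3 |

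The binomial standard error at 15% with n = 14 is √(0.15 × 0.85/14) = 9.5 points. At d = 10% the upward shift is 0.8 to 1.7 points; at d = 40% it is 5 to 10 points.

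**Decision rule, if the 15% null means all treated patients.** Put a into the exact binomial with n = 14:

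| | d = 0 | 10% | 20% | 30% | 40% |
|---|---|---|---|---|---|
| P(X ≥ 2), f = 0 | 64.3% | 70.4% | 76.9% | 83.5% | 89.9% |
| P(X ≥ 2), f = 0.5 | 64.3% | 67.5% | 71.1% | 75.3% | 80.2% |
| P(X ≥ 5), f = 0 | 4.67% | 6.90% | 10.45% | 16.24% | 25.85% |
| P(X ≥ 5), f = 0.5 | 4.67% | 5.72% | 7.21% | 9.45% | 12.98% |

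The cut-off of 5 is not in the plan. It is used only to show that correcting the rule in 10.1 would not remove this effect.

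**At trial size.** With 4 responders among 14 evaluable patients and 4 replaced patients without a response, the two denominators give 4/14 = 28.6% and 4/18 = 22.2%.

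**The compliance sentence.** Section 10.3.5 measures tablets taken against tablets expected, allowing for prescribed omissions. A patient stopped at day 10 for progression can be fully compliant, so 10.3.5 and 7.1 can both hold. They clash for a patient discontinued in cycle 1 under the 60% rule of 8.10: 10.3.5 sets no bar to including that patient, while 7.1 replaces the patient.

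**The 28 days.** Section 8.3 keeps cycle days running through held or missed doses. The plan does not say whether 28 days of drug means calendar days or dosing days.

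**The case against.** The strongest reply is that neither size nor direction is documented. No early-stop share is given for this regimen. Eligibility requires expected survival of at least 3 months, and grade 3 or 4 non-hematologic toxicity leads first to a hold (8.7.1). The only 28-day retention figure is in section 8.6: 6 of 9 patients, so 3 of 9 (33%) were not retained, but that is a pediatric glioma cohort on a different schedule. Some early leavers could be responders, through early transplant, an optional marrow (8.13), or hematologic improvement if 9.1 is read to count it. All of this stands. It limits the claim to a probable upward bias, material mainly at the higher shares.

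It can also be said that the statements of 14 fit together as a planned 14 with replacement. That reading is possible, but the plan does not state it, so the denominator is unclear rather than flatly contradictory.

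Three stronger readings might be inferred and are not supported. First, 10.3.5 does not contradict 7.1 for every early stop, as shown above. Second, the lack of a 28-day condition in 9.1 is not a conflict, because 9.1 defines responders and not the denominator. Third, early leavers are not left unassessed. Section 6.3.1 says "patients will be discontinued from the study drug but continued to be followed for survival data in the following circumstances" and refers them to the Study Schedule and section 11.1.7, which requires a 30-day evaluation; Appendix IV has end-of-study and follow-up columns. What stays open is only whether a response marrow is done after early stopping, since 8.12 confines the schedule to patients receiving drug and the marrow row of Appendix IV is not clearly legible in the text available.

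**Conclusion.** The concern holds in this form: replacement is blind to reason, no all-treated efficacy set or non-responder rule is defined, and following 7.1 probably raises the primary response rate. Under the assumed shares of 10 to 40% and a true rate of 15%, the rise is 1.7 to 10.0 points if all early leavers fail and 0.8 to 5.0 points if they respond at half the overall rate. It vanishes if they respond at the same rate and reverses if they respond more often.

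A reader might conclude that type I error is inflated. That follows only if the 15% null refers to all treated patients, which 10.1 does not say; if it refers to evaluable patients, the rule's error rate is not distorted by replacement. Confidence is high on the gap in the text and moderate on the direction; the size rests on assumption. For a study that calls itself a pilot, this should be fixed before analysis, but it does not by itself invalidate the design.

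**What to change.** Define the primary efficacy set as all patients who took at least one reinduction dose. Classify each on documented best response whatever the time on drug, and count those with none as non-responders. Apply the decision rule to that set, with a cut-off prespecified for each possible number treated. Report the set with at least 28 days as a labelled sensitivity analysis.

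In the same revision:
- Say whether 28 days means calendar or dosing days, given section 8.3.
- Align the Synopsis and sections 7.1, 7.2 and 10.1 on the denominator, and say which population the 15% and 30% describe.
- State whether patients enrolled under version 3.0 on the flat dose count toward the 14.
- State how 10.3.5 applies to patients stopped for noncompliance in cycle 1.
- Clarify, across 6.3.1, 8.12 and Appendix IV, whether a response marrow is done after early stopping.

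The cost is text, plus a somewhat lower reported rate, since a patient never assessed counts as a failure. Power falls if the 30% target was meant for evaluable patients. If all early leavers fail, the all-treated rate is 0.30(1 − d) = 27/24/21/18% at 10/20/30/40% early stops. With 14 treated, power of the written rule then falls from 95.3% to 92.5/88.4/82.6/74.7%, and that of the illustrative cut-off of 5 from 41.6% to 31.9/23.0/15.2/9.1%. Keeping a target power under a corrected rule could need more patients.
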